was rural households in the K-N District that used biofuels (wood, animal waste, and crop residue) as their main cooking fuel source, and that contained women and young children (demographic groups typically in closest proximity to cooking activities). Data from the HDSS enabled a cluster random selection of households from the district population that met the REACCTING eligibility criteria. The social structure in this region is such that groups of related households live in connected compounds. For the purposes of the HDSS, compounds are grouped into geographic **clusters**, with up to 99 compounds per cluster. These clusters are grouped into five geographic regions: four of these are primarily rural (North, East, South, and West), while the Central region contains Navrongo town and surrounding areas. For the REACCTING sample, we first eliminated households from the Central region, and then we randomly selected 25 clusters using population weighting to determine the number of clusters selected per region. Within each cluster, eight households were randomly selected from the population of households that met the study eligibility criteria, resulting in a total sample of 200 households.

[figure not shown]
The stove intervention of the REACCTING study includes four different intervention arms: Group A received two Gyapa stoves, Group B received two Philips stoves, Group C received one of each type of

stove, and Group D serves as the control for the duration of the study, but will receive their choice of stove at the conclusion of the study (the timing of which will coincide with the beginning of the research project described here). Stove stacking (i.e., households using new cookstoves alongside traditional cooking methods) had been observed in prior studies and we had earlier observed multiple stove use by the households in the study area. Multiple stoves were provided to each intervention household to increase the probability that households would begin to substitute away from traditional stoves rather than simply adding a new stove to their cooking technology mix. Randomization into intervention groups was done at the cluster level: i.e., within each of the 25 clusters, there are 2 households in each of the 4 REACCTING intervention groups.

REACCTING Preliminary Results

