The design of our intervention requires that we offer stoves that are similar to those offered for the REACCTING study, since we are measuring whether exposure to these technologies through peers influences adoption decisions. However, our experience in the REACCTING study revealed some key challenges with both the Gyapa and Philips stove models, such that we have elected to use slightly different stove models for this project. Through initial lab testing at CU as well as consultation with individuals in the study area, we have selected the Greenway Jumbo stove as a rocket-type stove, similar to the Gyapa, and the ACE1 stove as a forced-draft stove, similar to the Philips.

Peer Effects

Random variation in exposure to peers with cookstove experience will be accomplished through selection of S Group households that vary in terms of their proximity and social contacts with the R Group. The **S1** subgroup will be drawn from the same clusters as the R Group households (25 R Group clusters). S1 group households will thus be located in close physical proximity to R Group households with new stove experience, and are expected to have several social ties to these households. Meanwhile, the **S2** subgroup will consist of 25 clusters randomly selected from the area of the K-N Districts outside of a certain buffer distance from the R Group clusters. Data from the REACCTING study and additional pretesting will be used to select a buffer distance that minimizes the expected number of ties between R and S2 Group households; given that there are more than 300 clusters in the district and only 25 were included in the R Group, these ties are expected to be minimal (and will be measured as part of our data collection). Because the R Group clusters were randomly selected initially, and the S2 clusters will also be randomly selected, the study design ensures that in expectation the only differences between S1 and S2 group households is the former's higher level of exposure to peers with cookstove experience, enabling us to test the impacts of this exposure on our outcomes of interest (perceptions and technology adoption and use).

Prices

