Instrument-based measurements												
Data analysis												
Dissemination												
- Preparation of reports and peer-												
reviewed publications												
- Presentation at scientific												
conferences												
- Workshop in study area												

V. FUNDING

This research is being funded by the National Science Foundation's Economics program and the National Institutes of Health's Clean Cooking Implementation Science Network.

VI. ABOUT THE SUBJECTS

Component #1: P3 Bio

As shown in Figure 5, a total of 300 households will be enrolled in the P3 Bio component of the study. In each household, the primary cook (typically female, aged 18-55 years old) will serve as the main study participant. In households where another male household member makes financial decisions, we will conduct a secondary survey with this individual as well. We anticipate that all of these households will complete the study. The study population includes two main ethnic groups: Kasem and Nankam. The population will be split roughly evenly between these two groups.

Table 3: Subject Populations

Subject Population(s)	Number to be enrolled in each group
Group S1: Rural households from the same	150 households
clusters as REACCTING study households	

Group S2: Rural households from different150 householdsclusters from REACCTING study households150 households

Inclusion / Exclusion Criteria

Sample selection will proceed in two phases. First, clusters will be selected for inclusion in the study. All of the 25 REACCTING study clusters will be included to form the S1 group clusters. GIS mapping will then be used to *exclude* clusters that are close to those S1 clusters (using a buffer distance determined using preliminary data on social ties), and 25 S2 group clusters will then be randomly selected from the remaining clusters.

Second, the required number of households will be selected from each cluster. We will use the same inclusion and exclusion criteria used to select households in the existing REACCTING study. Using data from the district's demographic surveillance survey, a sample frame of eligible households will be created using the following inclusion criteria:

- Classified as "rural"
- Uses biofuel as main cooking fuel source
- Has woman in household aged 18-55 and at least one child under five (since women and children are the most vulnerable to cookstove smoke)

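### Drawing the S2 clusters only from outside a buffer makes their eligibility depend on location, so the design does not guarantee that peer exposure is the only expected S1-S2 difference

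*Combined protocol and SAP*

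**What the plan says.** **How S1 clusters arose.** Section III (REACCTING Study Sample and Intervention Design) says of the original draw that "we first eliminated households from the Central region", and that 25 clusters were then randomly selected "using population weighting to determine the number of clusters selected per region". Section VI (Inclusion / Exclusion Criteria) carries these over: "All of the 25 REACCTING study clusters will be included to form the S1 group clusters".

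**How S2 clusters arise.** Section IV (Peer Effects) describes "25 clusters randomly selected from the area of the K-N Districts outside of a certain buffer distance from the R Group clusters". Section VI says that clusters close to S1 are removed first, "using a buffer distance determined using preliminary data on social ties", and that "25 S2 group clusters will then be randomly selected from the remaining clusters". Neither place gives the buffer distance, a number of clusters per region, or a rule on Central clusters.

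**What is concluded.** Section IV states that "the study design ensures that in expectation the only differences between S1 and S2 group households is the former's higher level of exposure"; the exposure meant is contact with peers who have used the stoves.

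**What is held equal.** Households in both groups must meet the same eligibility criteria, including rural classification. They are picked by the same neighbour-of-a-seed procedure, with six seeds per cluster (Section VI). Ties between R and S2 households are to be measured (Section IV).

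**The concern.** Two random draws give equal groups in expectation when both use the same frame. Here the second frame is what is left after a distance filter centred on the first draw. Passing that filter depends on where a cluster lies: one in a dense neighbourhood is likely to fall near some R cluster, while an isolated or edge cluster is not.

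The S1-S2 contrast carries research questions 2 and 3 and three rows of Table 1. If density, remoteness or region affects adoption or perceptions by a route other than peers, such as fuel supply, market access or income, that effect is counted as a peer effect. More households would not remove it. Section II gives some reason to think that location matters in this district: about one third of the urban population uses LPG as main fuel, against 3% outside the central area. A similar link for biomass stoves is plausible, but the documents do not show it.

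**Working it through.** **1. The plan's own figure.** Table 1 gives power 0.838 for adoption of 75% in S2 against 60% in S1, with 147 per group. Alpha and sidedness are not stated. A one-sided 0.05 two-proportion test with continuity correction reproduces it:

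- corrected difference = 0.15 − 1/147 = 0.1432
- null SE = √(2 × 0.675 × 0.325 / 147) = 0.0546
- alternative SE = √((0.75 × 0.25 + 0.60 × 0.40) / 147) = 0.0539
- power = Φ((0.1432 − 1.645 × 0.0546) / 0.0539) = Φ(0.989) = 0.839

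This calculation takes the whole S1-S2 difference to be the peer effect.

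**2. Why eligibility depends on location.** Section IV supplies the counts: "given that there are more than 300 clusters in the district and only 25 were included in the R Group". Take 300 clusters and, for simplicity, one simple random draw of 25. A cluster that is not itself drawn and has k others within the buffer stays eligible for S2 with probability C(299 − k, 25) / C(299, 25).

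| k | 0 | 1 | 2 | 5 | 10 |
|---|---|---|---|---|---|
| probability of staying eligible | 1.00 | 0.92 | 0.84 | 0.64 | 0.41 |

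The chance of being drawn into S1 is 25/300 whatever k is. Unless every cluster has the same k, the two groups have different expected composition.

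**3. How large this could be.** The documents give no map or buffer, so the layouts are assumptions. In each run 300 clusters were placed, 25 R clusters drawn, and 25 S2 clusters drawn outside the buffer, with the same frame for both groups. There were 600 runs per setting, with buffers of 0.03 to 0.12 of the district side. The share removed is (275 − remaining) / 275. The shift is S2 minus S1 in number of neighbouring clusters, in SD units.

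| Assumed layout | Share of other clusters removed | Density shift |
|---|---|---|
| Regular grid | 0% to 61% | +0.01 to −0.19 |
| Uniform scatter | 7% to 64% | 0.00 to −0.32 |
| Dense core, sparse edge | 26% to 80% | −0.32 to −0.98 |

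In the dense-core layout S2 is also 0.27 to 1.34 SD farther from the centre.

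**4. Whether the design probability helps.** In half-clumped, half-uniform layouts, S2 clusters were weighted by the inverse of their probability of lying outside the buffer, obtained by redrawing the 25. Ranges are over repeated runs.

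| Share removed | Shift, unweighted | Shift, weighted |
|---|---|---|
| 15% to 17% | −0.12 to −0.14 | −0.01 |
| 25% to 26% | −0.19 to −0.24 | −0.01 to −0.03 |
| 43% to 45% | −0.38 to −0.44 | −0.03 to −0.06 |
| 60% to 62% | −0.49 to −0.59 | −0.12 to −0.16 |

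The 25 S2 clusters then act like about 24 at the smallest buffer and about 18 to 19 at the largest.

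**5. What an imbalance would do.** Suppose non-peer differences shift adoption by d around 67.5%, with 147 per group, a two-sided 0.05 test and clustering ignored. The chance of declaring a peer effect that does not exist is Φ((d − 1.96 × 0.0546)/SE) + Φ((−d − 1.96 × 0.0546)/SE), with SE about 0.054 to 0.055.

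| d | 2 points | 5 points | 10 points | 15 points |
|---|---|---|---|---|
| probability | 0.065 | 0.15 | 0.45 | 0.79 |

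Nothing in the documents converts a density shift into a value of d.

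**The case against.** **The S2 rules are silent, not contrary.** A reader might infer that S2 was drawn without regional allocation and with Central clusters included. The text says only that selection is random, so an allocation is unreported rather than ruled out. Section VI also says that the REACCTING household criteria are reused, and the Central exclusion was described at household level. But the listed criteria do not repeat it, so the point is open. This objection stands.

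**The direction is not fixed.** A reader might infer that S2 is systematically more isolated. With a common frame, the buffer pushes that way, but by close to nothing when clusters are evenly spaced and the buffer is small. If Central clusters were eligible for S2 only, the sign can reverse: on an assumed map with 60 of 300 clusters in a dense core, S2 came out 0.48 to 0.70 SD denser than S1. This stands too.

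**Non-random S1 status.** A reader might infer that adjustment cannot help because S1 and S2 were not randomised against each other. The R draw was random, so the probabilities are unequal but computable. That is why weighting works.

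**Research question 3.** A level shift that is the same at every price cancels in a true price-by-peer interaction. This is correct. However, the interaction row of Table 1 compares S1 with S2 within the P2 group, assuming full adoption at P0 in both, and a level shift enters that comparison directly.

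**Existing safeguards.** Matched household selection equalises sampling within clusters, not which clusters are sampled. Measured ties check contamination. Balancing prices across S1 and S2 protects the price contrast. The baseline survey and recorded coordinates make adjustment feasible, but no S1-S2 balance check or location adjustment is stated.

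**Conclusion.** The guarantee in Section IV does not follow from the plan's own selection rules. S1 and S2 can differ in expectation in density, remoteness and region, and nothing stated corrects this between clusters. With one frame for both groups, the illustrative shift in local density runs from about zero to several tenths of an SD, and to about 1 SD in a dense-core layout. These figures rest on assumed maps, buffers and a proxy for location. They show possible imbalance in a cluster characteristic, not a measured bias in adoption or perceptions. The documents do not support saying that S2 is in fact more isolated, that regional allocation was omitted, or that the peer estimate is biased by any given amount. The supported conclusion is that equality in expectation is not assured, that the cause is identifiable, and that most of it can be removed unless the buffer takes out a large share of clusters.

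**What to change.** 1. State the buffer distance, the number of S2 clusters per region, and whether Central clusters were eligible.
2. On the HDSS/GIS map, repeat the original 25-cluster draw many times with its regional allocation, and record how often each cluster lies outside the buffer. Use that probability as a weight or adjustment variable, together with region, in every S1-S2 comparison.
3. Report S1-S2 baseline balance on location (density, distance to town, region) and on household characteristics.
4. If S2 has not yet been drawn, use the same four-region frame and allocation as the REACCTING draw. The protocol is version 4, dated January 2018, in the third year of a timeline ending August 2018, so this may be too late. Items 1 to 3 remain available either way.
5. Replace the guarantee with a statement that S1 and S2 are comparable conditional on region and the probability of lying outside the buffer, with possible residual imbalance when the buffer removes a large share of clusters.

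**Cost.** A short simulation on the mapping data that the plan already relies on, and some precision in the S1-S2 contrast. In the illustration the loss is small at a narrow buffer (about 24 effective S2 clusters of 25) and appreciable at the widest (about 18 to 19).

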Since some households will be offered stoves for free while others will be offered stoves at positive prices, the benefits will be *unequal* across participants. However, these prices will be varied *at random*, such that the benefits will not be *inequitable*: at the outset of the study, all respondents will have an equal chance of being assigned to different price levels. This study design will be clearly explained to participants at the outset, as described in the Recruitment section (VIII) and specified in the Consent Form. Randomization of clusters to different price levels will be done in a participatory and transparent manner – for example, we may conduct the randomization during a meeting involving representatives from the different clusters, allowing these individuals to draw numbers out of a hat to determine their clusters' stove price levels, and videotaping this process so that it is available to show respondents concerned about the fairness of the price assignment.

Analysis of Key Research Questions and Power Calculations

Econometric analysis of data from the experiments will estimate regression models for three key outcome variables: stove adoption, use, and perceptions of quality (pre- and post-adoption). Multiple indicators of each of these outcomes will be possible. For example, adoption measures can include binary indicators for purchase / receipt of *any* stove, as well as indicators for the number and type(s) of stoves selected. Stove use measures will come from surveys and electronic monitors, and can be specified at the stove or household level over various time periods (e.g., reported use on previous day from survey vs number of uses over a month from SUMs). Perceptions measures can include overall favorable / unfavorable ratings as well as more continuous measures from Likert-scale and/or subjective expectation responses.

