Using the cluster-randomized assignment of selected households to different price treatments along with prior random selection of the REACCTING study clusters (and subsequent inclusion of non-REACCTING households), we will estimate a variety of reduced-form and potentially structural models using the exogenous variables of stove price, as well as cluster-level prior adoption and usage. These models will be used to investigate the validity of the broad conceptual model, to test specific research hypotheses emerging from the formal economic model in Section 4.1, and to explore additional research questions, including the relationship between perceived stove quality and instrument-based measures of personal exposure to emissions.

The study's power to detect significant effects will vary depending on the specific outcome variable used (e.g., easier to detect effects for continuous vs binary variables), the cell sizes (smaller for interactions than for main effects), and the effect sizes, which are always difficult to estimate *a priori*. Table 1 shows power estimates for a sample of possible analyses under different assumptions.

Effect	Outcome variable	Assumed effect size across	Power to
		groups being compared	detect
Main effect of price	Purchase / receipt of any stove by	100% in P0 (N=70) vs 75% in	0.999
on adoption	household (binary)	P1 (N=84)	
		100% in P0 (N=70) vs 50% in	0.999
		P2 (N=140)	
Main effect of price	Reported use of stove on day prior to	50% in P0 (N= 70) vs 75% in	0.965
on stove use	survey (binary)	P2 (N=140)	
		(positive price effect)	

Table 1: Power to detect sample of possible treatment effects under different assumptions

Main effect of price on perceived quality	Continuous stove quality index (0 to 100) from Likert-scale questions (Assuming normal dist. with std. dev. of 25 pts)	75 pts in P1 (N=84) vs 65 pts in P0 (N=70) (positive price effect)	0.800
Main effect of peers on adoption	Purchase / receipt of any stove by household (binary)	75% in S2 (N=147) vs 60% in S1 (N=147) (negative peer effect)	0.838
Main effect of peers on perceived quality	Continuous stove quality index (0 to 100) from Likert-scale questions (Assuming normal dist. with std. dev. of 25 pts)	50 pts in S1 (N=147) vs 60 pts in S2 (N=147) (negative peer effect)	0.96

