Interactive effect of peers' experience and price on adoption	Difference in purchase / receipt of any stove at high price between peer- exposed vs unexposed groups, assuming P0 adoption is 100% in S1 and S2	Within P2 group, 60% drop in demand in S1 (N=70) vs 40% drop in demand in S2 (N=70) (higher price elasticity within peer-exposed group)	0.7112

Component #2: Liquefied Petroleum Gas (LPG) - P3 Gas

Phase 1: Characterizing LPG Supply and Demand

Activity 1.1: LPG Supply Chain Analysis. Purpose: To describe the current LPG supply chain serving the K-N, including sources and costs of LPG stoves, cylinders, and fuel, and to analyze barriers and opportunities for scaling up and transforming the supply chain to expand access.

For this activity, we will identify all retail centers in the K-N selling LPG stoves or cylinders, as well as retail LPG filling stations throughout the Upper East region. Surveys will be conducted with all retail operators to measure: i) location (GPS coordinates), ii) type(s) of products sold; iii) hardware and fuel prices (measured at multiple time points to monitor price volatility); iii) sources of products and fuels supplying the retail center; iv) perceived problems or issues with the supply of products from the retailer's perspective, including uncertainty in supply or cost; v) perceived levels of demand in the local area and potential strategies for increasing demand, including price-related incentives and social or peer-to-peer marketing approaches; vi) potential opportunities and barriers for expanding operations into new areas, including peri-urban and rural areas; and v) potential for shifting to cylinder recirculation as opposed to the current cylinder refilling model.

Activity 1.2: LPG Demand Assessment. Purpose: To describe current patterns of LPG use for household cooking in the K-N, and to assess opportunities and barriers for expanding LPG adoption.

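### Table 1's price-on-use row counts all 140 P2 households, although two other rows of the table assume that only half of them take a stove

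*Combined protocol and SAP*

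**What the plan says.** All the figures are in Section IV, under Analysis of Key Research Questions and Power Calculations, in Table 1.

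- **Price on stove use.** The outcome is self-reported use of a stove on the day before the survey (binary). The contrast is "50% in P0 (N= 70) vs 75% in" P2, where the P2 number is 140. The row is labelled a positive price effect and gives power 0.965. It does not say whether the denominator is stove owners or all households offered a stove.
- **Price on adoption**, the row just above. The P2 contrast is "100% in P0 (N=70) vs 50% in" P2, again with 140 households.
- **Interaction of peers and price.** "Within P2 group, 60% drop in demand in S1 (N=70) vs 40% drop in demand in S2 (N=70"), "assuming P0 adoption is 100% in S1 and S2".

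The text introducing the table says: "Table 1 shows power estimates for a sample of possible analyses under different assumptions". The same section says that use measures "can be specified at the stove or household level over various time periods". Under Prices, a household may take no stove, one or two.

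**The concern.** A household that takes no stove cannot report using a new one. A use rate over all P2 households is therefore capped by P2 adoption, and a use rate among owners has only the adopters as its denominator. The row combines a rate of 75% with a denominator of 140, and at the 50% adoption assumed elsewhere in the table neither reading allows that.

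Use is one of the three key outcomes, and Section II presents the effect of price on use as an open question. The two possible contrasts answer different questions. Use among owners conditions on purchase, so it mixes the selection of keener buyers with any effect of having paid; Section II names allocation to those who value the good most as one of its two mechanisms. Use over all randomised households keeps the protection of the price randomisation. A reader should be able to see which of these the 0.965 describes.

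**Working it through.** **Inputs from Table 1.** Use 50% in P0 and 75% in P2; 70 and 140 households; P2 adoption 50% (adoption row); demand drops of 60% and 40% from 100% in two P2 halves of 70 (interaction row). **Assumed:** alpha 0.05, because the table gives neither alpha nor sidedness. P0 and P2 are read as the lowest and highest price cells.

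**Step 1. What 140 counts.** The price cells sum to 70 + 84 + 140 = 294, and the peer groups sum to 147 + 147 = 294. So 140 is the whole P2 cell.

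**Step 2. P2 adopters in the other rows.**
- Adoption row: 0.50 × 140 = 70.
- Interaction row: 0.40 × 70 + 0.60 × 70 = 28 + 42 = 70.

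**Step 3. Reproduce the stated power.** Two-proportion normal approximation with pooled null variance:

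power = Φ[(d − z·s0)/s1]

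- d = |p1 − p2| − ½(1/n1 + 1/n2); the second term is dropped without continuity correction
- s0 = √[p̄(1 − p̄)(1/n1 + 1/n2)]
- s1 = √[p1(1 − p1)/n1 + p2(1 − p2)/n2]

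For 70 and 140: d = 0.2393, p̄ = 0.6667, s0 = 0.0690, s1 = 0.0701. With z = 1.645, power = Φ(1.795) = 0.964, against 0.965 stated. The same method gives 0.839 for peers on adoption (stated 0.838), 0.714 for the interaction (stated 0.7112) and 0.999 for P0 against P1 adoption (stated 0.999). One-sided 5% with continuity correction is therefore the table's apparent method, and the row is computed correctly for its printed inputs.

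**Step 4. Owner reading.** With 70 and 70: d = 0.2357, p̄ = 0.625, s0 = 0.0818, s1 = 0.0791. With z = 1.645, power = Φ(1.279) = 0.900. The range by method and by assumed P2 adoption is:

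| P2 adoption | P2 owners | One-sided, corrected | Two-sided | Two-sided, corrected |
|---|---|---|---|---|
| 100% (what N = 140 would need) | 140 | 0.964 | 0.949 | 0.931 |
| 75% | 105 | 0.945 | 0.926 | 0.900 |
| 50% (adoption and interaction rows) | 70 | 0.900 | 0.872 | 0.830 |

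No figure allows for randomisation of price by cluster.

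**Step 5. All-household reading.** P2 use = adoption × use among adopters.
- To reach 75%, adoption must be at least 75%: 0.75 × 1.00, or 1.00 × 0.75 at the other end.
- At 50% adoption the maximum is 0.50 × 1.00 = 50%, equal to the P0 rate, so no positive difference is possible.
- Illustration only: 75% use among owners at 50% adoption gives 0.50 × 0.75 = 37.5% over all P2 households, below the 50% in P0. The two contrasts can differ in sign.

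**The case against.** The strongest reply is that the table's rows are offered as illustrations under differing assumptions and need not share one scenario. That is fair, and it limits the weight of the point. It does not rescue the row: 140 owners would need 100% adoption at P2, 75% of all households would need at least 75%, and no row assumes either. If a separate adoption rate was intended, stating it is the remedy.

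A second reply is that use might be counted per stove, or that any stove, traditional ones included, might qualify. The plan leaves the level of measurement open, so neither can be excluded as a future analysis. But 70 and 140 match the household cells. For 70 P2 owners to supply 140 stoves, each would have to take two, while each of the 70 P0 households took exactly one. An any-stove outcome would make 75% possible, but the row does not say so, and it would not measure use of the offered stoves.

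A third reply is that Section II points to use among those who own the product. It does lean that way, though the phrase about ownership there describes a cited bednet trial. If owners are meant, N = 140 is the figure to correct.

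It also stands that the cells are provisional: the design is called preliminary and replicates per price level await pretesting. No sample-size decision is shown to rest on this row.

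A reader might go further and combine the peers row, "75% in S2 (N=147) vs 60% in S1 (N=147) (negative peer effect"), with the P0 and P1 rates: 0.75 × 147 + 0.60 × 147 = 198.45 adopters, less 70 and 63, leaves 65.45, or 46.75% of 140. The documents do not support treating that as the assumed P2 adoption, because it joins rows presented as separate illustrations. The point rests only on the 50%, which is printed in one row and follows directly from another.

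**Conclusion.** The concern holds in a limited form. The stated 0.965 requires all 140 P2 households in the denominator, while the adoption and interaction rows both put P2 adoption at 50%. For owners at that rate, power is about 0.90 by the table's apparent method, 0.87 two-sided and 0.83 two-sided with correction, given assumed alpha 0.05 and no clustering allowance. For new-stove use over all offered households, the assumed 75% is out of reach at 50% adoption.

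Two stronger conclusions are tempting and unsupported. The row is not miscalculated, since it reproduces from its printed inputs. Nor does it show that the study is underpowered for use: the loss on the owner reading is modest, and every figure at 70 owners stays above 0.80 before clustering.

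**What to change.** In the price-on-use row, name the population and the assumed P2 adoption rate. If the population is owners, replace 140 with the implied number of owners (70 at 50%, updated when the price cells are final) and restate the power with its alpha and sidedness. If a different adoption rate was intended, state it and make N and the use rate agree with it.

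Because the owner contrast conditions on purchase, add a sentence saying so. Also report use over all randomised households, counting non-owners as not using the new stove. This fits the reduced-form price models already planned and uses the endline survey in Section XII. The investigators can choose which contrast is main.

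The cost is one table row and a few sentences, with no new data. The stated power becomes somewhat less favourable.
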